4. STUDY DESIGN

4.1. Overall Design

213500 (SOLAR – Switch Onto Long Acting Regimen) is a Phase IIIb, randomized, open-label, active-controlled, multicenter, parallel-group, non-inferiority study designed to assess the antiviral activity and safety of a two-drug regimen of CAB LA + RPV LA administered every 2 months compared with maintenance of BIK. Approximately 654 adult HIV-1 infected patients who are on the stable ARV regimen BIK will be randomized 2:1 to either be switched to the CAB LA + RPV LA regimen or continue current ART through 12 months. The study will continue with an Extension Phase after Month 12 (OLI and BIK)/Month 11 (D2I).

Participants will be randomized (2:1) at Day 1 to either discontinue BIK and either choose to begin oral therapy with CAB 30 mg + RPV 25 mg once daily to determine individual tolerability, prior to administration of CAB LA + RPV LA, or transition directly to injections, or continue on BIK. Current ART dosing on Day 1 is not

recommended to occur after randomization to avoid overlap of regimens (in the event that the participant is assigned to the CAB LA + RPV LA treatment arm). However, if the participant takes BIK prior to coming into the clinic, randomization and initiation of oral CAB and RPV or injections should continue as planned for Day 1.

For those randomized to receive CAB + RPV and choose to begin the oral lead in, at the Month 1 visit, safety assessments (including e.g., clinical chemistries) will be performed as per the SoA (Section 1.3). At visit Month 1, participants will return to the clinic, take the last dose of oral CAB + RPV, and receive the first CAB LA (600 mg) + RPV LA (900 mg) injections (within 2 hours of the final oral dose of CAB + RPV). The first injection visit (Month 1) can be performed before central lab results are available and safety parameters are reviewed. If a retest is required based on Month 1 labs, the retest should be performed as soon as possible (and preferably no later than 7 days following Month 1). Those participants who choose to start injections immediately will receive the first CAB LA (600 mg) + RPV LA (900 mg) injections on Day 1.

Randomization will be stratified by gender at birth and BMI. The primary endpoint for the study is the proportion of participants with plasma HIV-1 RNA ≥ 50 c/mL who meet the ≥ 50 c/mL criteria at Month 12. The proportion of participants with plasma HIV-1 RNA < 50 c/mL at Month 12 using the FDA Snapshot algorithm (Missing, Switch or Discontinuation = Failure, Intent-to-Treat Exposed [ITT-E] population) is a key secondary endpoint.

A total of 654 participants with a 2:1 randomization ratio to either CAB LA+RPV LA or BIK is such that the study has approximately 85% power to demonstrate non-inferiority in the proportion of participants with snapshot virologic failure at Month 12 using a 4% margin, assuming a true 2% failure rate for CAB LA + RPV LA and a 1% failure rate for the BIK arm using a 2.5% one-sided alpha level. The randomized portion of the study will continue for 12 months with an Extension Phase.

No dose reductions, modifications, or changes in the frequency of any components of each regimen will be allowed during this study, except those allowed and defined in the protocol. Protocol waivers or exemptions are not allowed. Therefore, adherence to the study design requirements, including those specified in the SoA (Section 1.3), are essential and required for study conduct. If deviations are required for the management of immediate safety concerns, these should be communicated promptly to the study medical monitor.

4.1.1. Screening Phase (up to 35 days)

Informed consent must be obtained prior to any study procedures, including any Screening assessment.

Participants will complete a screening period of up to 35 days. A single repeat of a procedure/lab parameter is allowed to determine eligibility (unless otherwise specified). In exceptional circumstances only, if a repeat lab is required because a central lab result cannot be generated, local labs can be reviewed and approved by the Medical Monitor for consideration of participant eligibility. A repeat central lab will be submitted concurrently or at the next planned visit. Participants may be re-screened once which

requires a new participant number. Participants who are randomized into the trial and subsequently withdrawn from the study, for any reason, may not be re-screened. Participants may be randomized as soon as all eligibility requirements have been confirmed at the site.

4.1.2. Maintenance Phase

At Day 1, eligible participants will be randomized 2:1 to either the CAB LA + RPV LA Q2M arm or the BIK arm. For participants who are randomized to the CAB LA + RPV LA arm, they will be able to choose to begin oral therapy with CAB 30 mg + RPV 25 mg once daily to determine individual safety and tolerability, prior to administration of CAB LA + RPV LA or transition directly to injections:

Oral Lead In

Participants will remain on oral BIK until the Day 1 visit, and until any required Screening visit retest results are available for review. On Day 1, participants who choose to participate in the oral lead in will be administered oral CAB 30 mg + RPV 25 mg once daily for one month (participants will be assessed for tolerability after one month). At Month 1, participants will have the assessments completed as per the SoA (Section 1.3.), including clinical chemistries. The participant will take the last dose of oral CAB + RPV, and to receive the first CAB LA + RPV LA injections (within 2 hours of the final oral dose). The first injection visit with IM CAB LA 600 mg and RPV LA 900 mg can be performed before central lab results are available and safety parameters are reviewed. The second IM injection with CAB LA 600 mg and RPV LA 900 mg will be performed at Month 2 with a visit window of -7 days allowed. **Receiving LA dosing up to +7 days is not recommended and the Medical Monitor must be contacted.** Subsequent injections with CAB LA 600 mg and RPV LA 900 mg will occur every 2 months thereafter, from the projected visit date, with a dosing window of ± 7 days allowed. If the injection is expected to fall outside of the dosing window, the Medical Monitor must be contacted to discuss individual participant case management.

Direct to Inject (no oral lead-in)

Central lab results (or local lab results if a central lab is not available) and safety parameters from the Screening visit must be available and reviewed for participants who choose to transition directly to injections without an oral lead-in. Participants with ongoing safety issues or laboratory abnormalities of clinical concern (e.g. Grade 3 or Grade 4 liver chemistry elevations) will require consultation and agreement with the Medical Monitor prior to proceeding directly to injections in the Maintenance Phase. If a clinical chemistry retest is required based on Screening visit labs, the retest should be performed as soon as possible (and preferably no later than 7 days following the Screening visit). Participants will remain on BIK until the Day 1 injection visit, and until any required Screening visit retest results are available for review.

At Day 1, eligible participants will take the last dose of BIK and receive the first injections of CAB LA (600 mg) + RPV LA (900 mg) as initial loading doses. Clinical chemistries will also be obtained at Day 1. The second and third injections (CAB LA 600 mg + RPV LA 900 mg) will be administered at Month 1 and Month 3. The second IM injection with CAB LA 600 mg and RPV LA 900 mg will be performed at Month 1 with a visit window of -7-days. For the second IM injection, a visit window for **LA dosing from +1 to +7 days is not recommended and the Medical Monitor must be contacted** before the second IM injection is given. Subsequent injections (CAB LA 600 mg + RPV LA 900 mg) will occur every 2 months thereafter, from the projected visit date, with a ± 7 -day dosing window being allowed. If the injection is expected to fall outside of the dosing window, the Medical Monitor must be contacted to discuss individual participant case management.

Note: Study participants with \geq Grade 1 ALT at screening and or Day 1 must be discussed with the Medical Monitor prior to initiation of LA dosing; continuation in the study or progression onto LA dosing may require additional evaluations, including labs drawn after a period of oral dosing with CAB + RPV.

BIK

Continue on current ART (BIK) regimen for 12 months. Participants who successfully complete Month 12 (without meeting study defined withdrawal criteria and who remain virologically suppressed (HIV-1 RNA <50 c/mL) will be given the option to switch to the LA arm in the Extension Phase (with or without an OLI) or to successfully complete and withdraw from the study (no withdrawal visit needed).

4.1.3. Extension Phase

All eligible participants who transition into the Extension Phase will continue study treatment until CAB LA and RPV LA are either locally approved and commercially available, the participant no longer derives clinical benefit, the participant meets a protocol-defined reason for discontinuation or until development of either CAB LA or RPV LA is terminated. Visits will continue to occur every 2 months.

Participants not eligible to enter the Extension Phase will end their study participation. Sites may be reimbursed for up to a one-month supply of antiretroviral medication to facilitate transition to non-study ART for participants that do not qualify for the Extension Phase.

NOTE: the transition plan to marketed product (either CAB+RPV LA or alternative HAART) should be done in consultation with the Central Study Team and the Medical Monitor. Participants with ongoing safety issues or laboratory abnormalities of clinical concern (e.g. Grade 3 or Grade 4 liver chemistry elevations) will require consultation and agreement with the Medical Monitor prior to proceeding to commercial supply.

4.1.3.1. Participants Entering from the CAB LA + RPV LA Arm

All participants who successfully complete 12 months of CAB LA + RPV LA treatment in the Maintenance Phase will continue to have access to both CAB LA and RPV LA in the Extension Phase. See the SoA (Section 1.3) for more information.

4.1.3.2. Participants Entering from the BIK Arm

Participants randomized to continue BIK will have the option to either continue study participation by switching to CAB LA + RPV LA in the Extension Phase, or to complete their study participation at Month 12 (no withdrawal visit needed). The transition from BIK to CAB LA + RPV LA within the Extension Phase can be completed with or without an oral lead-in prior to commencement of injectable treatment. The participant's decision will be taken in consultation with the investigator and must be appropriately documented. As participants approach the Month 13 visit, sites must ensure sufficient CAB and RPV supply are available to support the participant's decision for transition to LA.

Participants who choose to continue on to the Extension Phase will need to be assessed for eligibility to begin the CAB LA + RPV LA regimen. Participants will continue on BIK while eligibility is being confirmed.

All participants with an undetectable HIV-1 RNA (<50 c/mL) result from the Month 12 visit are eligible to enter the Extension Phase. A single repeat of HIV-1 RNA for any participant with a HIV-1 RNA ≥ 50 c/mL and < 400 c/mL at Month 12 must be performed. The retest should be scheduled as soon as possible (but no later than 4 weeks from the Month 12 visit). Participants with a HIV-1 RNA <50 c/mL upon retest are eligible to enter the Extension Phase. Participants with HIV-1 RNA ≥ 400 c/mL at Month 12 are not eligible to enter the Extension Phase, will not be allowed a repeat to determine eligibility, and will therefore be withdrawn from the study.

Result of HIV-1 RNA at Month 12	Action
<50 c/mL	Begin Extension Phase for participants randomized to BIK at Month 13
≥ 50 c/mL but <400 c/mL	Perform HIV-1 RNA retest as soon as possible (not later than 4 weeks).
Single repeat <50 c/mL	Begin Extension Phase for participants randomized to BIK at Month 13
Single repeat ≥ 50 c/mL	Cannot begin Extension Phase and must be withdrawn from study; Complete withdrawal visit
≥ 400 c/mL	Cannot begin Extension Phase and must be withdrawn from study; Complete withdrawal visit.

Please refer to Section 6.11.1 for a list of prohibited medications concurrent with either formulation for CAB and/or RPV.

Participants Transitioning Direct to Injection in the Extension Phase:

Central lab results (or local lab results if a central lab is not available) and safety parameters from the Month 12 visit must be available and reviewed for participants who choose to transition directly to injections. Participants with ongoing safety issues or laboratory abnormalities of clinical concern (e.g. Grade 3 or Grade 4 liver chemistry elevations) will require consultation and agreement with the Medical Monitor prior to proceeding directly to injections in the Extension Phase.

If a clinical chemistry retest is required based on Month 12 labs, the retest should be performed as soon as possible (and preferably no later than 7 days following Month 12). Participants will remain on oral BIK until the Month 13 injection visit, and until any required Month 12 retest results are available for review.

At Month 13, eligible participants will take the last dose of BIK and receive the first injections of CAB LA (600 mg) + RPV LA (900 mg) as initial loading doses. Clinical chemistries and safety assessments will also be obtained at Month 13. The second injection (CAB LA 600 mg + RPV LA 900 mg) will be administered at Month 14, with a visit window of -7-days. **Receiving LA dosing from +1 to +7 days is not recommended and the Medical Monitor must be contacted before the next injection is given.** Subsequent injections (CAB LA 600 mg + RPV LA 900 mg) will occur every 2 months thereafter, from the projected visit date, with a ± 7 -day dosing window being

allowed. If the injection is expected to fall outside of the dosing window, the Medical Monitor must be contacted to discuss individual participant case management.

Participants Receiving Optional Oral Lead-In in the Extension Phase:

As participants approach the Month 13 visit, sites must ensure sufficient oral CAB and RPV are available for participants who choose to use the oral lead-in.

At Month 13, eligible participants who after discussion with the investigator, choose to receive the optional oral lead-in will initiate a 4-week lead-in of oral CAB 30 mg + oral RPV 25 mg once daily. It is not necessary to dose BIK on the day the participant begins the oral lead-in with CAB + RPV. However, if the participant takes BIK prior to coming into the clinic, initiation of oral CAB and RPV should continue as planned. Clinical chemistries will be assessed at Month 13. At Month 14, following the 4-week CAB + RPV oral lead-in, participants will have additional safety assessments including clinical chemistries as per the SoA (Section 1.3). At the Month 14 visit, participants will take the last dose of oral CAB + RPV and receive the first CAB LA (600 mg) + RPV LA (900 mg) injections (within 2 hours of the final oral dose of CAB + RPV). The first injections can be performed before central lab results become available and safety parameters are reviewed. The second injection (CAB LA 600 mg + RPV LA 900 mg) will be administered at Month 15 with a - 7-day window being allowed. **Receiving LA dosing up to +7 days is not recommended and the Medical Monitor must be contacted.**

Subsequent injections (CAB LA 600 mg + RPV LA 900 mg) will occur every 2 months (bi-monthly) thereafter, from the projected visit date, with a ± 7 -day dosing window being allowed. If the injection is expected to fall outside of the dosing window, the Medical Monitor must be contacted to discuss individual participant case management.

4.1.4. LTFU Phase – IM Regimen Only

Any participant who receives at least one dose of CAB LA and/or RPV LA and discontinues the CAB LA + RPV LA regimen for any reason must remain on suppressive HAART for at least 52 weeks after the last dose of CAB LA and/or RPV LA in order to prevent selective pressure on HIV and the potential for selection of resistant mutants.

Investigators must discuss the choice of the follow-up HAART regimen with the Medical Monitor prior to initiating the new regimen with the participant. HAART therapy should be initiated within 8 weeks (± 7 days) after the last Q2M injection.

The LTFU will begin the day of the last CAB LA and/or RPV LA dose and continue for 52 weeks, or until the assigned CAB LA + RPV LA regimen is locally approved and commercially available. These participants will complete Withdrawal assessments and will then enter into the LTFU as per the Time and Events Schedule. In addition, for participants who withdraw during the LTFU, the final visit will be considered the study withdrawal visit.

After receiving at least one dose of LA CAB and LA RPV, participants who decide to no longer continue with LA dosing for whatever reason must transition to the 52 week long term follow up (LTFU) phase of SOLAR. These participants are considered on study but off IP and should return for follow up visits at 3, 6, 9 and 12 months after the last LA was administered. Female participants of child bearing potential must continue to use adequate

contraception methods (see Study Procedures Manual for list of accepted forms of contraception) for the entire year of follow up.

In order to assure that participants have access to HAART during the LTFU, ViiV may supply HAART regionally or reimbursement will be provided as needed during this phase. The LTFU Phase may be shortened or terminated at any time during the study for various reasons, e.g., better understanding of risks of development of resistance as CAB and RPV exposures decline, regulatory approval and commercial availability, end of study timings, etc. If the participant is administered an ABC-containing product, see Section 8.3.11.8.

This phase is considered study participation and participants will be followed on study during this time. A withdrawal visit is not required for participants who do not complete the LTFU Phase. The participants' last on study visit will be considered as their withdrawal visit.

Participants who are randomized to LA CAB and LA RPV and chose to perform the Oral Lead In and decide not to continue while performing the Oral Lead in are not required to enter the LTFU.

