	
4 weeks of fetal development (at which time the neural tubes are sealed) this potential risk would concern women exposed to DTG at the time of conception and in early pregnancy. Recently updated data (April 2020) for this birth outcome study showed that among women who were on DTG when they became pregnant, 7/3591 NTD occurred (0.19%). In comparison, NTDs were identified in 21/19,361 (0.11%) women delivering on any non-DTG antiretrovirals. There was not a significant difference in the number of NTDs between births to women taking DTG and those taking other non-DTG antiretroviral treatments (0.09% difference).
 
The clinical relevance of either of these findings in relation to CAB use is unknown.
	
periods despite discontinuation of CAB LA.
 
 Participants who become pregnant during the study may remain in the study, provided that all protocol defined pregnancy related assessments, procedures and documentation are completed and a pregnancy specific ICF addendum is signed by the participant. Details regarding management of pregnant participants is found in Appendix 6.

Development of Resistance following discontinuation of CAB LA
	
Residual concentrations of CAB would remain in the systemic circulation for prolonged periods (more than 1 year in some cases) in participants who stop CAB LA treatment, (e.g., for tolerability issues or treatment failure).
 
Participants discontinuing CAB LA regimen may therefore be at risk for developing HIV-1 resistance to CAB after discontinuing injectable therapy.
	
 After participants stop CAB LA, Oral HAART regimens will be prescribed within 8 weeks after the last Q2M dose, and following consultation with the medical monitor. This would be anticipated to result in continued suppression or rapid resuppression of HIV-1 RNA thus minimizing the risk of emergent resistance The participants in this study who discontinue IM CAB for any reason will be monitored for a

Potential Risk of Clinical Significance	Summary of Data/Rationale for Risk	Mitigation Strategy
		
minimum of 52 weeks from the time of the last IM CAB injection.

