6.9.1. IM Dosing

Participants receiving CAB LA and/or RPV LA are anticipated to be at risk for development of virologic resistance if ART is interrupted. The time period during which participants are at risk for development of virologic resistance may be determined by the period between when drug levels fall below therapeutic values and when they fall below levels which exert selective pressure on HIV. This time period will vary by ART agent and is dependent upon effective concentration, inhibitory concentration, and half-life. Plasma concentrations of both LA drugs may be measurable for more than one year following IM injections. Any interruption in IM dosing should be discussed with the Medical Monitor. Investigators should ensure that the participant initiates alternative highly active ART to minimize the risk of developing resistance as concentrations of CAB and RPV decline over time.

IM dosing is expected to occur during the week in which the participant's projected visit falls (as according to the date of the first injection). The first injections for participants who choose to start injections immediately will occur at Day 1. The first injections for participants electing to participate in the oral lead are administered at Month 1 (can be performed before lab results become available), and the second injections are given at Month 2.

The participant's projected visit is determined by their first injection date and, ideally, is the same date for every injection. For example, if the 1st dose (Month 1) is January 15th, then dose 2 (Month 2) will be February 15th, and dose 3 (Month 4) will be April 15th, etc.

Since the first injection visit (Day 1 or Month 1) will determine the future injection visit schedule for participants, planning for the first injection visit date (within allowed visit windows) should take into consideration the availability of the participants to adhere to future visit windows (planned vacations, business trips, weekends, holidays, *etc.*).

Dosing for participants randomized to CAB LA + RPV LA is as follows:

All injections should be planned as single injections per drug.

6.9.1.1. IM injections every 2 months (Oral Lead In):

Month 1 – CAB LA 600 mg + RPV LA 900 mg IM, each given as 1 X 3 mL IM injection

Month 2 - CAB LA 600 mg + RPV LA 900 mg IM, each given as 1 X 3 mL IM injection

Month 4 and Q2M thereafter - CAB LA 600 mg + RPV LA 900 mg IM, every 2 months until Month 12, each given as 1 X 3 mL IM injection

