At Month 1, participants will return to the clinic, take the last dose of their oral (CAB 30 mg + RPV 25 mg), and receive the first CAB LA (600 mg) + RPV LA (900 mg) injections (within 2 hours of the final oral dose of CAB + RPV). The first injection visit

with IM CAB LA + RPV LA at Month 1 can be performed before central lab results are available and safety parameters are reviewed from the Month 1 visit.

The second loading injection will be administered at Month 2 (CAB LA 600 mg + RPV LA 900 mg), with subsequent injections (CAB LA 600 mg + RPV LA 900 mg) occurring every 2 months thereafter. A -7-day dosing window for the second injection is allowed.

Receiving LA dosing from +1 to +7 days is not recommended and the Medical Monitor must be contacted before the second IM injection is given. Starting at Month 4 and at subsequent visits, a ± 7 -day dosing window for injections is allowed. If the injection is expected to fall outside of the dosing window, the Medical Monitor must be contacted to discuss individual participant case management.

6.9.1.2. IM injections every 2 months (Q2M) (Direct to injections):

Participants electing not to receive the oral lead in and are receiving CAB LA + RPV LA Q2M will initiate dosing at the Day 1 visit:

Day 1- CAB LA 600 mg + RPV LA 900 mg IM, each given as 1 X 3 mL IM injection

Month 1 and Q2M thereafter- CAB LA 600 mg + RPV LA 900 mg IM, each given as 1 X 3 mL IM injection

The second injection will be administered at Month 1 (CAB LA 600 mg + RPV LA 900 mg), with subsequent injections (CAB LA 600 mg + RPV LA 900 mg) every 2 months thereafter. A -7-day dosing window for the second injection is allowed.

Receiving LA dosing from +1 to +7 days is not recommended and the Medical Monitor must be contacted before the second IM injection is given. Starting at Month 3 (third injection) and every 2 months thereafter, a ± 7 -day dosing window for injections is allowed. If the injection is expected to fall outside of the dosing window, the Medical Monitor must be contacted to discuss individual participant case management.

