- For any participant who withdraws prematurely from the Maintenance or Extension Phase during a planned in-clinic study visit, withdrawal assessments and procedures are to be performed (according to the SoA (Section 1.3) instead of the assessments for the active planned visit during which the withdrawal decision is made.

Withdrawal decision occurs between planned clinic visits:

- In the event that a decision to withdraw a participant occurs between clinic visits, participants will be instructed to return for an unscheduled withdrawal visit (within 8 weeks of the last Q2M LA injection received or within 4 weeks if participant is randomised to BIK or during the administration of the OLI (oral CAB and oral RPV) if randomized to CAB LA + RPV LA and choosing to perform the OLI) during which withdrawal assessments according to the SoA (Section 1.3) will be completed. For participants who received one or more injections of CAB LA+ RPV LA **withdrawal assessments must occur prior to initiation of the next ART regimen.**

If withdrawal coincides with the active planned Month 13 visit, HIV-1 RNA will only be assessed if the last HIV-RNA measurement from Month 12 was ≥ 50 copies per mL (i.e. retest for viral load blip). This will ensure that only the Month 12 viral load assessment or required retest will be counted towards the primary and secondary efficacy endpoint windows.

The in-clinic visit will be recorded as an unscheduled withdrawal visit with the following exception. A withdrawal visit and assessments coinciding with the planned Month 13 visit will be recorded as the Month 13 visit such that the participant can be considered a completer, consistent with the definition of study completer in Section 4.5.

Participants may be prematurely discontinued from the study treatment for any of the following reasons:

- Adverse event / Serious adverse event
- Protocol deviation
- Intolerability of injections
- Participant lost to follow-up
- Participant or Investigator non-compliance;
- Termination of the study by the Sponsor
- At the request of the participant, Investigator, GSK or ViiV Healthcare;
- The participant requires concurrent prohibited medications during the course of the study. The participant may remain in the study if in the opinion of the Investigator and the medical monitor; such medication will not interfere with the conduct or interpretation of the study or compromise the safety of the participant.

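### The time limit for starting oral HAART after the last injection differs between protocol sections and does not match the protocol's own dosing intervals

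*Protocol*

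**What the plan says.** Four places in the protocol bear on the limit.

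- **Section 4.1.4 (LTFU Phase).** The scope is "Any participant who receives at least one dose of CAB LA and/or RPV LA and discontinues" the regimen. The limit is that "HAART therapy should be initiated within 8 weeks", plus or minus 7 days, counted from the last Q2M injection.
- **Section 2.3.1 (Risk Assessment), resistance rows for CAB LA and for RPV LA.** As mitigation, "Oral HAART regimens will be prescribed within 8 weeks after the last Q2M dose". Neither row gives an allowance.
- **Section 7.1, decision to withdraw between planned visits.** The participant returns for an unscheduled visit "within 8 weeks of the last Q2M LA injection received", again with no allowance. For those who have had an injection, "withdrawal assessments must occur prior to initiation of the next ART regimen". For a decision made at a planned visit, Section 7.1 sets no day limit.

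The dosing calendar is in Sections 4.1.2, 6.4 and 6.9.1. The second injection is due one month after the first, with an early window of 7 days only. On lateness, Section 6.9.1 says "Receiving LA dosing from +1 to +7 days is not recommended and the Medical Monitor must be contacted". From the third injection the interval is two months, plus or minus 7 days. Months are calendar months: "if the 1st dose (Month 1) is January 15th, then dose 2 (Month 2) will be February 15th", and the third dose in that example is on 15 April.

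**The concern.** Section 2.3.1 offers the HAART limit as the mitigation against resistance while drug levels decline after injections stop, and Section 6.9.1 gives the same reason for starting alternative therapy. A safeguard of this kind should read the same wherever it appears and should fit the schedule that it follows. Here the allowance is present in one section and absent in the others. Eight weeks is used although dosing is by calendar month, and Section 4.4.1.2 itself treats 8-weekly and two-monthly dosing as different schedules (7 against 6.5 doses in year 1). One limit is also stated for everyone, although the interval after the first injection is half as long as the later ones. Sites could apply different limits to the same participant. For someone who stops after one injection, the text either permits a start well after the missed dose was due or says nothing.

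**Working it through.** The protocol gives no derivation of the 8 weeks, so there is no figure to reproduce. The check is calendar arithmetic.

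**Inputs**
- Limit without allowance (Section 2.3.1; also the Section 7.1 visit limit): 8 × 7 = 56 days.
- Limit with the allowance at its later end (Section 4.1.4): 56 + 7 = 63 days.
- First to second injection (Sections 4.1.2 and 6.9.1): one calendar month, 28 to 31 days.
- Later injections (Section 6.9.1): two calendar months. 15 January to 15 March is 59 days in a non-leap year; 15 July to 15 September is 62. Every first-injection date from November 2020 to December 2024 (an assumed range that includes a leap year) gives 59 to 62 days.
- Permitted late window for those injections: +7 days, so 59 + 7 = 66 to 62 + 7 = 69 days.

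**(a) Stopping after the first injection.** Days from the due date of the missed second injection to the HAART limit = limit − interval.
- Limit of 56: 56 − 31 = 25 to 56 − 28 = 28 days.
- Limit of 63: 63 − 31 = 32 to 63 − 28 = 35 days.

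The limit therefore falls 25 to 35 days after the next dose was due, whereas one day late for that dose already calls for contact with the Medical Monitor. An unscheduled withdrawal visit under Section 7.1 may also fall as late as day 56.

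This assumes that the first injection counts as a Q2M injection. Section 6.9.1 lists it under the two-monthly schedule, but Section 6.4 labels it a loading dose and reserves Q2M for the injections after it. On the second reading, no limit is stated for this participant.

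**(b) Withdrawing at a planned Q2M visit.** HAART cannot start before the withdrawal assessments, so its earliest start is the visit day.

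| Visit | Day | Against 56 (Section 2.3.1) | Against 63 (Section 4.1.4) |
|---|---|---|---|
| On time | 59 to 62 | 3 to 6 days past | 1 to 4 days to spare |
| +7 days | 66 to 69 | 10 to 13 days past | 3 to 6 days past |

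On-time visits meet day 63 on every date checked and never meet day 56. Among visits 2, 3 and 4 days late, 83.8%, 16.6% and 12.3% still meet day 63. From 5 days late none does, because 59 + 5 = 64.

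**The case against.** The strongest reply is that 8 weeks is an outer limit and not a schedule, and that other provisions surround it. Interruptions of injections are to be discussed with the Medical Monitor and alternative therapy ensured (Section 6.9.1), an unannounced missed dose requires contact for guidance (Section 6.12), and the choice of HAART is discussed with the Medical Monitor (Section 4.1.4). A due date for an injection and an outer limit for starting oral therapy are also different rules, and whether they should coincide is a clinical judgement. All of that stands. It does not remove the difference in allowance between sections or settle which limit applies after a first injection, and none of those provisions states another time limit.

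Four stronger inferences are tempting, and the protocol does not support them.

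- *On-time Q2M withdrawals cannot comply and are automatic deviations.* Under Section 4.1.4 every on-time visit is within day 63, and nothing prevents HAART from starting on the visit day. The shortfall exists only against the unqualified 8 weeks of Section 2.3.1, or late in the permitted window.
- *The 8-week visit limit in Section 7.1 is breached by planned-visit withdrawals.* That limit applies only to decisions made between planned visits.
- *Participants are left without drug.* Section 6.9.1 notes that concentrations may be measurable for more than a year. Table 2 reports no trough later than 4 weeks after an initiation injection given alone, and the simulated profiles in Figures 3 and 4 are not shown in the text at hand. The supportable statement is that the limit lies past the protocol's own next due dose.
- *The secondary resistance endpoint is biased.* That endpoint serves an objective about participants with confirmed virologic failure (Section 3). LTFU starts on the day of the last long-acting dose (Section 4.1.4), and the failure definition does not apply in LTFU (Section 7.1.7). Harm to the endpoint is not shown.

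**Conclusion.** The inconsistency is real. The first-injection case is the more important part: the limit as written lies 25 to 35 days past the protocol's own next due dose, or no limit is stated, depending on whether the first injection counts as a Q2M injection. The Q2M case is a consistency error. An on-time withdrawal visit is 3 to 6 days past the limit in Section 2.3.1 yet inside the limit in Section 4.1.4, and a visit at the end of the allowed window is past both. The figures rest on same-date calendar dosing, as in the protocol's own example, and on reading the allowance in Section 4.1.4 as extending the limit to day 63. The finding concerns the wording of a stated safety measure. It does not show an effect on the primary analysis or on the secondary resistance endpoint.

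**What to change.** Reconcile Section 2.3.1 (CAB LA and RPV LA rows), Section 4.1.4 and Section 7.1 with each other and with the dosing intervals in Sections 4.1.2 and 6.9.1. After the change:

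- the limit and its allowance should agree wherever they appear;
- it should be clear which limit applies to a participant whose only injection is the first;
- the withdrawal visit should be able to precede HAART within the limit, including for visits inside the permitted dosing window.

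The sponsor's clinical team decides the figures and the rule; none is proposed here. The cost is a wording change in four places, by amendment or clarification, with no extra visits or participants.
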